## 11.2 Analysis variables

### 11.2.1 General

**Baseline value** is defined as the last non-missing value before date and time of first dose intake of double-blind treatment.

**Analysis value** is defined as the value at the visit (numeric result in standard units).

**Absolute change from baseline** is defined as post-baseline value minus baseline value, i.e., a positive sign indicates an increase as compared to baseline.

**Percent change from baseline** is defined as the absolute change from baseline divided by the baseline value (if the baseline value is  $> 0$ ) and then multiplied by 100.

**Ratio to baseline** is defined as the value at the visit divided by the value at baseline (if the baseline value is  $> 0$ ).

**Analysis Date** is defined as the numeric SAS date derived from the Date/Time of assessment. It can be an imputed date [cf. section 12 for more details].

**Analysis Start Date** is defined as the numeric SAS date derived from the Start Date/Time of an event. It can be an imputed date [cf. section 12 for more details].

**Analysis End Date** is defined as the numeric SAS date derived from the End Date/Time of an event. It can be an imputed date [cf. section 12 for more details].

**Analysis End Relative Day** is estimated for several assessments, including AE end, treatment interruptions, concomitant medication end. It refers to the number of days between the end of the specific event and the first study treatment intake.

### 11.2.2 Subject Level Data

This dataset regroups information from Demographics (DM), Disposition (DS), Death Details (DD), Vital Signs (VS), Exposure (EX), Subject Visits (SV), Reproductive System (RP), Substance Use (SU) domains and their supplemental domains.

#### *Subject demographics*

**Age, Age Units, Sex:** retrieved from the DM domain or, in case of re-screening, retrieved from the supplemental domain.

**Childbearing potential:** latest information to be retrieved from the RP domain (the information recorded for a RE-SCREENING supersedes information collected at SCREENING).

**Race, Ethnicity, Country:** the information has to be retrieved from the DM domain. Variables to facilitate the production of the summary tables have to be created (e.g., numeric code to enable the correct display order or the long value in proper case).

Variables related to substance use (**Smoking habits, Number of cigarettes smoked, Number of years quit, Year quit**) are retrieved from Substance Use domain.

**Weight (kg) and Height (cm) at baseline:** the latest information has to be retrieved from the VS domain (prior to first intake).

***Population flags***

**Screened Subject Flag** is assigned to Y for all subjects who have a record in the DM domain.

**Re-Screened Subject Flag** is assigned to:

- Y for subjects who have a record in the SV domain with a visit number equal to 1.1
- N otherwise.

**Randomized Population Flag** is assigned to:

- Y for all subjects who have a record in DS domain with a Standardized Disposition Term equal to RANDOMIZED
- N otherwise.

**Full Analysis Set Population Flag** is assigned to:

- Y for all subjects who have a record in DS domain with a Standardized Disposition Term equal to RANDOMIZED
- N otherwise.

**Safety Analysis Set Population Flag** is assigned to

- Y for all subjects who have a record in EX domain corresponding to the first study treatment administration (Group ID =DAY 1 /RE-INITIATION)
- N otherwise.

**Per-protocol Population Flag** is assigned to:

- Y for all subjects included in the Full Analysis Set who have no record in the DV domain flagged as 'leading to exclusion from PPS'
- N otherwise.

**Pharmacokinetic Analysis Set Population Flag** is assigned to:

- Y for all subjects included in the Safety Analysis Set who have at least one non-missing ACT-33341 concentration available post-baseline
- N otherwise.

**Pharmacodynamic Analysis Set Population Flag** is assigned to:

- Y for all subjects:
  - included in the Safety Analysis Set,
  - with an available baseline value for lymphocyte count (from a sample taken from ICF through first study treatment),
  - with an available post-baseline value for lymphocyte count (from a sample taken at least 21 days after the first study treatment intake but no later than 7 days after the last study treatment without treatment interruption documented in the first 3 weeks).
- N otherwise.

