### 4 CHANGES OR CLARIFICATIONS TO ANALYSES PLANNED IN THE STUDY PROTOCOL

#### 4.1 Changes to the analyses planned in the study protocol

##### 4.1.1 Pharmacodynamic analysis set definition

Previously Read

The pharmacodynamics analysis set (PDS) includes all subjects who received at least 3 weeks of study treatment and have at least one lymphocyte count measurement between the Week 4 visit and Week 12 visit.

Now Reads:

The pharmacodynamics analysis set (PDS) includes all subjects who received at least 21 days of uninterrupted study treatment, with lymphocyte count measurements at baseline and post-baseline (namely, one sample taken at least 21 days after the first study treatment intake and no later than 7 days after the last study treatment intake and no study treatment interruption documented in the first 21 days).

Rationale for change:

To allow analysis of the primary endpoint, the change from baseline to end of treatment (EOT) in lymphocyte count, based on a value at baseline and a value 'under treatment' so that the expected drug dependent effect on the lymphocyte count is biologically meaningful and has sufficient time to reach the full effect on lymphocyte reduction.

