#### 7.1.3 Per-protocol analysis set

The Per-Protocol Set (PPS) comprises data from all subjects included in the FAS without relevant deviations which could affect the evaluation of the PD parameters (lymphocyte count) and the exploratory disease activity parameters (SLEDAI-2K, PGA).

The protocol deviations leading to exclusion from the PPS are listed in the below table.

Please note:

- If a subject is excluded from the PDS then he is also excluded from the PPS.  
*Rationale:* Insufficient pharmacodynamic effect is unlikely to show e.g. clinical improvement, but will confound the results.
- [REDACTED] If a subject presents with such protocol deviation (specifically, pregnancy test not performed 3 weeks apart), but no pregnancy occurred and all subsequent pregnancy tests were consistently negative during the trial, the subject can be included into the PPS.  
*Rationale:* Biologically this subject is not different from included subjects. However, an important protocol deviation has to be reported.
- [REDACTED]: If a subject presents with such protocol deviation, but the change of the immunologically active medication occurred at or after EOT, the subject can be included in the PPS.  
*Rationale:* The primary endpoint compares the change from baseline to EOT.

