#### 7.1.5 Other analysis sets

##### 7.1.5.1 Pharmacodynamic Analysis Set

The Pharmacodynamics Analysis Set (PDS) includes all subjects who received at least 21 days of study treatment, with lymphocyte count measurements at baseline and post-baseline (namely, one sample taken at least 21 days after the first study treatment intake and no later than 7 days after the last study treatment intake with no treatment interruption documented in the first 21 days).

Subjects are analyzed according to the treatment received.

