### **Additional expressions**

#### **End of treatment (EOT)**

For analyses ran on the FAS or the SAF, an additional observation (AVISITN = 6.1, AVISIT = 'End-of-treatment', DTTYPE = 'LOCF') is created for all subjects with at least one post-baseline assessment available. It is populated with the latest non-missing value assigned from analysis visit Week 2 to analysis visit Week 12 according to the LOCF principle.

In addition, for analyses ran on the PDS or the PPS, an extra observation (AVISITN = 6.2, AVISIT = 'End-of-treatment', DTTYPE = 'LOCF') is created for all subjects with at least one non-missing post-baseline assessment performed at least 21 days after the first study treatment intake but no later than 7 days after the last study treatment intake. It is populated with the latest value available fitting these criteria.

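### The SAP's PDS flag and its end-of-treatment record omit the 21-day treatment requirement in the PDS definition, so a permanent stopper with 15-20 days of dosing can enter the main lymphocyte analysis

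*SAP*

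**What the plan says.** The definition of the PDS has two parts. Section 7.1.5.1 of the SAP says the set "includes all subjects who received at least 21 days of study treatment, with lymphocyte count measurements at baseline and post-baseline", and then describes which sample counts. Section 4.1.1, which records the change from the protocol, asks for "at least 21 days of uninterrupted study treatment". Its rationale is that the value should be taken under treatment, after enough time for the full lymphocyte effect.

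Section 11.2.2 (Population flags) turns this into a derivation. It requires Safety Analysis Set membership, a baseline count, a post-baseline "sample taken at least 21 days after the first study treatment intake but no later than 7 days after the last study treatment", and no interruption documented in the first 3 weeks. Section 11.1.1 creates the EOT record for the PDS and PPS (AVISITN 6.2) from an assessment "performed at least 21 days after the first study treatment intake but no later than 7 days after the last study treatment intake". Neither mentions treatment duration, and nor does the EOT definition in Section 5.5.1.

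Section 10.6.3 runs the main MCP-Mod and ANCOVA analysis on the PDS. Section 10.6.2 justifies carrying early values forward by Phase 1 profiles that levelled off at 20-23 days of treatment.

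On the per-protocol set, Sections 7.1.3 and 11.2.3 both say: "If a subject is excluded from the PDS then he is also excluded from the PPS". The PPS flag in 11.2.2 takes Full Analysis Set subjects "who have no record in the DV domain flagged as" leading to PPS exclusion. It does not name the PDS.

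**The concern.** The derivation is what gets programmed. If it is looser than the definition, membership of the main analysis set depends on which section the programmer follows. The condition that drops out is the one the SAP introduced to make sure the analysed value reflects enough dosing. A subject on active drug who stopped before the plateau would contribute a value expected, if anything, to lie closer to placebo, in an arm planned at 12 subjects.

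Such stops can arise from the protocol itself. Under Protocol Table 2, a fall of more than 15% in FEV1 or FVC at Week 2 leads to a repeat test, preferably within a week, and to permanent discontinuation if confirmed. With the Week 2 visit on Day 15 and a repeat within 7 days, the stop falls at about Days 15-22.

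**Working it through.** The documents give no figure for how many subjects this affects, so there is none to reproduce. The check is whether the gap exists, how wide it is, and how much exposure is lost.

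**Inputs.**
- Day 1 is the day of first intake, so 21 days after first intake is Day 22 (SAP 11.1.1).
- Treatment duration is last intake minus first intake plus 1, so a last dose on Day L means L days (SAP 11.2.5.1).
- An interruption is a treatment end recorded as temporary (SAP 5.3.4). Permanent discontinuation is handled separately (SAP 5.3.3).
- After a premature stop, the EOT visit is within 7 days of last intake (Protocol 5.1.9) and preferably 1 day after it (Protocol 8.2.4).
- The multiple-dose half-life is 12-22 days (Protocol 1.3.2.1).

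**Which stoppers pass.** For last dose on Day L and sample on Day S, with no temporary interruption, the flag needs S - 1 ≥ 21 and S - L ≤ 7. The definition also needs L ≥ 21.

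| Last dose | Sample days passing the flag | Days after last dose | Days treated |
|---|---|---|---|
| 15 | 22 | 7 | 15 |
| 16 | 22-23 | 6-7 | 16 |
| 17 | 22-24 | 5-7 | 17 |
| 18 | 22-25 | 4-7 | 18 |
| 19 | 22-26 | 3-7 | 19 |
| 20 | 22-27 | 2-7 | 20 |

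This gives 1 + 2 + 3 + 4 + 5 + 6 = 21 day pairs that pass the flag and fail the definition. The exposures of 15-20 days lie below, or at the lower edge of, the 20-23 day range in Section 10.6.2. If the 21 days were counted inclusively, the gap would be Days 14-20. Adding a duration of at least 21 days removes every one of these cases.

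**Loss of exposure (assumed model).** Assume one-compartment kinetics with daily dosing and k = ln 2 / half-life. The fair comparator is the least-exposed subject the definition admits: last dose Day 21, sampled Day 28. For a last dose on Day L sampled 7 days later, the concentration ratio is (1 - e^(-kL)) / (1 - e^(-21k)).
- L = 15: 0.580 / 0.703 = 0.82 (12 days); 0.377 / 0.484 = 0.78 (22 days).
- L = 20: 0.685 / 0.703 = 0.97 (12 days); 0.467 / 0.484 = 0.97 (22 days).

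The range is about 78-97%.

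**Check on the model.** Accumulation by Day 35 is (1 - e^(-35k)) / (1 - e^(-k)), which is about 15-fold at 12 days and 22-fold at 22 days. Protocol 1.3.2.1 reports 5- to 9-fold. Choosing k so that steady-state accumulation 1 / (1 - e^(-k)) equals 5 or 9 gives 97% or 91% for L = 15. The 78% figure is therefore probably pessimistic. All of these are concentrations; the documents give no link from concentration to lymphocyte count.

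**PPS.** Section 11.2.3 repeats the rule beside the deviations dataset that the PPS flag reads. Nothing visible says that a PDS exclusion creates a flagged deviation record. The code table is not shown, so this cannot be settled either way.

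**The case against.** The best defence is that the no-interruption condition covers the case, since a subject who stops on Day 15 has not had three uninterrupted weeks. The SAP's own definition in Section 5.3.4 defeats this: only temporary interruptions count, and a permanent stop is recorded elsewhere.

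Several limits on the point do stand.
- The gap is narrow. A Day 15-20 stopper sampled at the preferred 1 day after the last dose is sampled on Days 16-21 and fails the flag. Some subjects in the spirometry pathway will reach 21 days before the repeat test stops them.
- Any effect is dilution towards placebo. The Week 12 complete-case analysis in Section 10.6.2 leaves these subjects out. The FAS repeat in Section 10.6.4 includes them by design, so it does not isolate the problem.

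A reader might go further and infer any of three things that the documents do not support.
- *That the PPS flag also lets early stoppers into the main analysis.* It cannot, because that analysis uses the PDS. Nor would a PDS test in the PPS flag remove them while the PDS flag still passes them. For the lymphocyte EOT value in the PPS, Section 5.5.1 already carries a no-interruption condition.
- *That the flag brings in subjects who are off drug.* The definition itself allows a sample up to 7 days after the last dose. With a 12-22 day half-life, about 67-80% of the last concentration remains at 7 days. The fault is short exposure.
- *That exposure is cut to 58-64% of the 21-dose level, or 34-41% of the Week 12 level.* Those ratios reproduce for a Day 15 stop sampled on Day 22. They are the worst of the 21 day pairs, they charge the permitted 7-day lag to the missing condition, and they rest on a model that over-predicts the reported accumulation.

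**Conclusion.** The PDS flag and the 6.2 record do not implement the PDS definition. Permanent stoppers with a last dose on Days 15-20 and a sample on Day 22 or later, 2-7 days after that dose, enter the main analysis against the set's own rule. This follows from the text and the SAP's day count and needs no modelling.

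The consequence is probably small. The direction is slight attenuation in the active arms. Each affected subject is one of 12 planned per dose (1/12 = 8% of an arm), and the modelled exposure is about 78-97% of the lowest the definition accepts. That range assumes one-compartment kinetics and is not a lymphocyte effect. The count of such subjects is not given and may be zero, so no effect on the estimate or on power can be computed.

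The PPS point is a missing cross-reference, not a demonstrated error, and bears on PPS analyses only.

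**What to change.** In SAP Section 11.2.2, add to the PDS flag that study treatment duration excluding interruptions, as derived in Section 11.2.5.1, is at least 21 days. Put the same condition on the AVISITN 6.2 record in Section 11.1.1.

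As a secondary edit, make the PPS flag require PDS flag = Y as well as FAS membership and no flagged deviation. The rule in Sections 7.1.3 and 11.2.3 then no longer depends on a deviation record having been created. This edit removes Day 15-20 stoppers from the PPS only if the PDS flag is corrected too.

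The cost is a few lines of derivation text using an existing variable, with no new data. The downside is that a few subjects may leave the PDS, as its definition already intends.

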#### *Treatment variables*

**Randomization Number** is extracted from the DS domain, from the Reference ID variable, for records with a Standardized Disposition Term equal to RANDOMIZED.

**Planned Arm Code, Description of Planned Arm, Actual Arm Code and Description of Actual Arm** are retrieved from the DM domain.

The actual treatment variables are derived similarly to the planned treatment variables according to the following table:

| Planned Arm Code | Description of Planned Arm | Planned Treatment for Period 01 (N) | Planned Treatment for Period 01 | Planned Dose for Period 01 |
|------------------|----------------------------|-------------------------------------|---------------------------------|----------------------------|
| A                | ACT-334441 0.5mg           | 2                                   | ACT-334441 0.5 mg               | 0.5                        |
| B                | ACT-334441 1.0 mg          | 3                                   | ACT-334441 1.0 mg               | 1.0                        |
| C                | ACT-334441 2mg             | 4                                   | ACT-334441 2.0 mg               | 2.0                        |
| D                | Placebo Control (Part A)   | 1                                   | Placebo                         | 0                          |
| E                | ACT-334441 4mg             | 5                                   | ACT-334441 4.0 mg               | 4.0                        |
| F                | Placebo Control (Part B)   | 1                                   | Placebo                         | 0                          |

#### *Trial dates*

**Date of Informed Consent Obtained** is extracted from the DS domain.

**Date of Randomization** is extracted from the DS domain.

**Date/time of Randomization** is extracted from the DS domain.

**Date of First Exposure to Treatment** is defined as the date/time of first study drug intake. It is the earliest treatment start date/time recorded in the EX domain.

**Date of Last Exposure to Treatment** is the date/time of last double-blind drug intake. It is the latest treatment end date/time recorded in the EX domain.

### ***Death variables***

**Date of Death** is extracted from the DS domain, where there is a record with Standardized Disposition Term equal to DEATH.

**Death Relative Day to EOT** is computed as the number of days between the date of first exposure to treatment and the end of treatment date.

**Death Relative Day** is computed as the number of days between the date of first exposure to treatment and the date of death.

**Death Dictionary-Derived Term** is extracted from the Death Details domain. It is equal to 'Character Result/Finding in Std Format' where Death Detail Assessment Name equals to Primary Diagnosis.

**Death Reported Term** is extracted from the Death Details domain. It is equal to Result or Finding as Collected where Death Detail Assessment Name equals to Primary Diagnosis.

### ***Screening variables***

**Date of Screening** is extracted from the SV domain as the start date of visit 1.

**Date of Screen Failure** is extracted from the DS domain.

**Reason for Screen Failure** is extracted from the DS domain. It is equal to:

- Subject withdrew consent, when there is a record with subcategory equal to RANDOMIZATION and a Standardized Disposition Term equal to WITHDRAWAL BY SUBJECT,
- Subject not eligible, when there is a corresponding record in the DS domain with a Standardized Disposition Term equal to SCREEN FAILURE and a Reported Term equal to NOT ELIGIBLE PER INCLUSION/EXCLUSION CRITERIA,
- Other, when there is a corresponding record in the DS domain with a category equal to OTHER EVENT and a Standardized Disposition Term equal to OTHER.

**Reason Spec for Screen Failure** is extracted from the DS domain. It is equal to the Reported Term from the record with a category equal to OTHER EVENT and a Standardized Disposition Term equal to OTHER.

*Conditional (if there is at least one re-screening visit performed)*

**Date of Re-Screening** is extracted from the SV domain as the start date of visit 1.1

### ***End of treatment variables***

**End of Treatment Date** is derived from DS domain where category equals to DISPOSITION EVENT epoch equals to TREATMENT.

**End of Treatment Day** is computed as the number of days between the date of first exposure to treatment and the end of treatment date.

**End of Treatment Status** is defined as Completed, Discontinued or *Ongoing*. It is equal to:

- *Ongoing, as long as there is no corresponding record in the DS domain*
- Completed, when there is a corresponding record in the DS domain with a Standardized Disposition Term equals to COMPLETED
- Discontinued, when there is a corresponding record in the DS domain with a Standardized Disposition Term not equals to COMPLETED.

#### ***End of study variables***

**End of Study Date** is derived from DS domain where category equals to DISPOSITION EVENT, subcategory equals to STUDY and epoch equals to FOLLOW-UP.

**End of Study Day** is computed as the number of days between the date of first exposure to treatment and the end of study date.

**End of Study Status** is defined as Completed, Discontinued or *Ongoing*. It is equal to:

- *Ongoing, as long as there is no corresponding record in the DS domain*
- Completed, when there is a corresponding record in the DS domain with a Standardized Disposition Term equals to COMPLETED
- Discontinued, when there is a corresponding record in the DS domain with a Standardized Disposition Term not equals to COMPLETED.

#### ***Accidental unblinding variables***

**Unblinding category** is populated, if there is a record in DS with a Standardized Disposition Term equals to equal UNBLINDED TREATMENT, with the contents of the Category for Disposition Event.

**Unblinding date/ time** is populated, if there is a record in DS with a Standardized Disposition Term equals to equal UNBLINDED TREATMENT, with the contents of the Start date/ time of the Disposition Event.

[figure not shown]
**Event that Triggered the Request** is populated, if there is a record in DS with a Standardized Disposition Term equals to equal UNBLINDED TREATMENT, with the contents of the Reported Term for the Disposition Event.

[figure not shown]
**Action Taken Following the Unblinding** is populated, if there is a record in DS with a Standardized Disposition Term equals to equal UNBLINDED TREATMENT, with the Data Value where the Variable Qualifier Name is equal to DSACNOTH.

[figure not shown]
#### **11.2.3 Protocol Deviations Data**

This dataset contains information from Protocol Deviations (DV) Domain and its supplemental domain, in an Occurrence Data Structure (OCCDS).

The presence of deviations affecting the assessment the efficacy leads to exclusion from the PPS. The following codes have been selected:

Please note:

- If a subject is excluded from the PDS then he is also excluded from the PPS.  
*Rationale:* Insufficient pharmacodynamic effect is unlikely to show e.g. clinical improvement, but will confound the results.
- [REDACTED] If a subject presents with such protocol deviation (specifically, pregnancy test not performed 3 weeks apart), but no pregnancy occurred and all subsequent pregnancy tests were consistently negative during the trial, the subject can be included into the PPS.  
*Rationale:* Biologically this subject is not different from included subjects. However, an important protocol deviation has to be reported.
- [REDACTED]: If a subject presents with such protocol deviation, but the change of the immunologically active medication occurred at or after EOT, the subject can be included in the PPS.  
*Rationale:* The primary endpoint compares the change from baseline to EOT.

